2.4.6.2 Pharmacodynamics [REDACTED] analyses

All biomarkers listed in Section 2.1.6 will be summarized in the Safety population defined as patients who actually received at least 1 dose or part of a dose of the IMP. Baseline values will be the last value collected prior to the first IMP. Descriptive statistics (including number, mean, SD, median, Q1, Q3, min, max) of biomarkers at baseline will be summarized.

Summary plots (mean +/- standard error of the mean) on values at each visit, absolute changes from baseline and percent changes from baseline will be provided for each biomarker by treatment group.

[REDACTED]

2.4.7 Analyses of health economics variables

Analyses of healthcare resource utilization will be performed under the responsibility of the Health Economics Outcomes Research (HEOR) department of Sanofi. Methods and results will be made available in a separate report.

2.5 DATA HANDLING CONVENTIONS

2.5.1 General conventions

The following formulas will be used for computation of parameters.

Demographic formulas

Age is calculated as:

$$\text{Integer part of (informed consent date - birth date)/365.25}$$

Age of onset of nasal polyposis is calculated as:

$$\text{Integer part of (nasal polyposis diagnosis date - birth date)/365.25}$$

Age of onset of asthma is calculated as:

$$\text{Integer part of (asthma diagnosis date - birth date)/365.25}$$

BMI is calculated as:

$$\text{Weight in kg / (height}^2 \text{ in meters)}$$

Renal function formulas

For patients ≥ 18 years old, creatinine clearance (CLcr) value will be derived using the equation of Cockcroft and Gault:

$$\text{CLcr (ml/min)} = (140 - \text{age}) \times \text{weight (kg)} \times (1 - 0.15 \times \text{sex (0-M, 1-F)}) / (0.814 \times \text{creatinine} \\ (\mu\text{mol/l}))$$

CLcr will be calculated using the last weight measurement on or before the visit of the creatinine measurement and age at the lab sampling date. Here age is calculated as following:

$$\text{Age} = \text{integer part of (lab sampling date - birth date)/365.25}$$

2.5.2 Data handling conventions for secondary efficacy variables

Periodical average of daily efficacy endpoints at designated study days

For the daily efficacy endpoints, the time period used to calculate the periodical average at each designated study day is summarized in [Table 2](#). Randomization day is used as the reference day (Day 1).

Table 2 - Periodical average of daily efficacy assessment

Time point	Morning TSS and its components (nasal congestion, loss of smell, anterior rhinorrhea, posterior rhinorrhea)	Morning NPIF
Day 29	2-29	2-29
Day 57	30-57	30-57
Day 113	86-113	86-113
Day 169	142-169	142-169
Day 281	254-281	-
Day 365	338-365	-
Day 449	422-449	-

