2.1.3.1 Primary efficacy endpoint(s)

There are 2 co-primary endpoints for this study for all countries except for Japan:

1. **Change from baseline in the nasal congestion/obstruction (NC) score at Week 24:** The NC score is assessed by the patient on a daily basis from V1 and throughout the study, using an e-diary, on a 0-3 categorical scale (1):

Nasal congestion/obstruction will be scored as a reflective score (evaluation of symptom severity over the past 24 hours) by the patient:

Scale	Symptoms
0	No symptoms
1	Mild symptoms (symptoms clearly present, but minimal awareness and easily tolerated)
2	Moderate symptoms (definite awareness of symptoms that is bothersome but tolerable)
3	Severe symptoms (symptoms that are hard to tolerate, cause interference with activities or daily living)

The e-diary is dispensed at V1 and information is downloaded from this device on the other indicated visit days as specified in the protocol.

A severity ≥ 2 on V1 and a weekly average severity greater than 1 at time of randomization (V2) is required for patient eligibility.

For baseline calculation (used to determine eligibility and to assess efficacy),

- if 4 or more measurements collected within 7 days prior to randomization are available, the baseline will be the average of these measurements;
- if less than 4 measurements are collected within 7 days prior to randomization, the baseline will be the average of the most recent 4 measurements prior to randomization (between V1 and V2).

For the baseline to EOT analysis, the average of all scores from the preceding 4 weeks to the corresponding visit will be used as the analysis score for that visit.

2. **Change from baseline in the NPS at Week 24:** The NPS (2)(3)(4) is assessed by centralized scoring of nasal endoscopy video recordings. The score (NPS) is the sum of the right and left nostril scores, as evaluated by means of nasal endoscopy. NP is graded based on polyp size described below.

Polyp Score	Polyp Size
0	No polyps
1	Small polyps in the middle meatus not reaching below the inferior border of the middle turbinate
2	Polyps reaching below the lower border of the middle turbinate
3	Large polyps reaching the lower border of the inferior turbinate or polyps medial to the middle turbinate
4	Large polyps causing complete obstruction of the inferior nasal cavity

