2.4.4.1 Analysis of primary efficacy endpoint(s)

Co-primary efficacy variables

The co-primary efficacy variables are: change from baseline in NC and in NPS (change from baseline in NC, NPS and LMK for Japan) at Week 24 assessed for dupilumab 300 mg q2w (pooled A and B arms) versus placebo, respectively.

The following null hypothesis and alternative will be tested for pooled dupilumab arms against placebo:

- H0: No treatment difference between the dupilumab dose regimen and placebo.
- H1: There is a treatment difference between the dupilumab dose regimen and placebo

Primary statistical model (ITT analysis)

Each of the 2 co-primary efficacy endpoints (3 co-primary efficacy endpoints for Japan) will be analyzed using a hybrid method of the worst-observation carried forward (WOCF) and multiple imputation. Data collected after treatment discontinuation will be included in the analysis. With this approach, for patients who undergo surgery for NP or receive SCS for any reason, data collected postsurgery (actual date) or post SCS will be set to missing, and the worst postbaseline value on or before the time of surgery or SCS will be used to impute missing Week 24 value (for patients whose postbaseline values are all missing, the baseline will be used to impute). For patients who discontinue the treatment without being rescued by surgery or receiving SCS, a multiple imputation approach will be used to impute missing Week 24 value, and this multiple imputation will use all patients who have not been rescued by surgery or receiving SCS at Week 24. Each of the imputed complete data will be analyzed by fitting an ANCOVA model with the baseline value of the corresponding co-primary endpoint, treatment group, asthma/NERD status, prior surgery history, and regions as covariates. Statistical inference obtained from all imputed data will be combined using Rubin's rule. Descriptive statistics including number of patients, mean, standard error, and least squares (LS) means will be provided. In addition, difference in LS means and the corresponding 95% confidence intervals (CI) will be provided along with the p-values.

Imputation and analysis model will be built with the following sample SAS code:

1. 40 datasets with a monotone missing pattern will be obtained, induced by Markov Chain Monte Carlo (MCMC) method on patients who have not been rescued by surgery or receiving SCS at Week 24.

```
proc mi data=dat_etd seed=14280 nimpute=40 out=dat_mc;  

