  mcmc impute=monotone;  
  var asthma surgery region treatment basenps chg4nps chg8nps  
  chg16nps chg24nps;  
run;
```

2. For each of the imputed dataset with monotone missing pattern in step 1, the remaining missing data will be imputed using the regression method for the monotone pattern with adjustment for covariates including treatment groups, region, asthma/NERD strata, surgery strata and baseline value of the response variable.

```
proc mi data=dat_mc nimpute=1 seed=14280 out=dat_mi;  
  by _imputation_;  
  class asthma surgery region treatment;  
  monotone method=reg;  
  var asthma surgery region treatment basenps chg4nps chg8nps chg16  
  nps chg24nps;  
run;
```

3. Each of the 40 imputed datasets will be merged with the one dataset imputed by WOCF approach, and then be analyzed using the main statistical model. These 40 imputed datasets will be saved.

```
%macro w1;  
  %do i=1%to 40;  
    data wocf&i.;  
    set wocf;  
    _imputation_=&i.;  
    run;  
  %end;  
  data wocf_all;  
  set %do j=1 %to 40; wocf&j. %end;;  
  run;  
%mend w1;  
  
%w1  
  
data dat_imp;  
  set dat_mi wocf_all;  
Run;  
  
proc sort data=dat_imp;  
  by _imputation_;  
run;  
  
proc glm data= dat_imp;  
  by _imputation_;  
  class region asthma surgery treatment;  
  model = chg24nps = basenps asthma surgery region treatment;  
  lsmeans treatment / stderr;  
  estimate 'Diff Dupilumab vs Placebo' treatment -1 1;  
  ods output LSMeans=implsmeans Estimates=implsmeandiff;  
run;
```

4. Applying Rubin's rule to combine analysis results (point estimates and standard errors) from 40 imputations using PROC MIANALYZE for the LS means and difference in LS means between dupilumab and placebo. Sample code:

```
proc sort data=implsMeans; by trt01pn _imputation_;run;

proc mianalyze data= implsmeans;
  by trt01pn;
  modeleffects lsmean;
  stderr stderr;
  ods output ParameterEstimates=lsmeans;
run;

proc mianalyze data=implsmeandiff;
  modeleffects estimate;
  stderr stderr;
  ods output ParameterEstimates=lsmeandiff;
run;
```

Sensitivity analysis

For all sensitivity approaches, for patients who undergo surgery for NP or receive SCS for any reason, data collected post surgery or post SCS will be set to missing

Mixed-effect model with repeated measures (MMRM) approach

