Justification: The primary analysis uses the mean. Assuming the NC symptoms are reasonably stable during these 7 days (observed in ACT12340), it deemed to be appropriate to use median here. Using median instead of mean is also in accordance with the ordinal categorical data nature of nasal congestion score.

- b. Week 24: for each day during study day 142 to study day 169, the change from baseline in scores will be re-coded as
 - i. =1 if a subject improves at least 1 category at that day.
 - ii. =0 if a subject does not improve at least 1 category at that day.

For a patient with observations during days 142 to 169 (28 days), he would have daily symptom improvement score as a 28-dimensional vector. Each element of the vector represents whether the subject shows improved symptom in nasal congestion on that day compared with baseline.

Missing data in any day during study day 142 to study day 169 will be imputed as not improved for that day (=0).

By such an approach, daily data are used in the model, and such data also preserve the categorical data nature of nasal congestion score. This approach gives statistical inference in terms of rate difference and has been theoretically and quantitatively validated (13).

In this model, factors (fixed effects) for treatment, stratification factors (region, co-morbid asthma/NERD and prior surgery), day, treatment-by-day interaction, baseline value as a categorical variable will be included. Generalized estimating equations (GEE) will be used to obtain statistical inference. A variance component working covariance matrix which is merely a weight matrix will be used in the model to obtain unweighted proportions. Descriptive statistics including number of patients, LS average proportion of patients with improvement across the 28 days, and corresponding standard error will be provided. In addition, difference in LS average proportion of patients with improvement, the corresponding 95% CI and the p-value will be provided for comparison of dupilumab against placebo.

Subgroup analyses

To assess the consistency in treatment effects across different subgroup levels, subgroup analyses will be conducted for the co-primary efficacy endpoints with respect to

- Age group (<65, ≥65 years)
- Gender (Male, Female)
- Region (Asia: Japan; Latin America: Argentina, Chile and Mexico; East Europe: Russia, Turkey; Western Countries: Australia, Belgium, Spain, Israel, Portugal, Sweden, Canada, USA)

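### A third of the diary days to Week 24 enter no 4-week average, so missing nasal congestion values would be imputed without the collected data closest to them

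*SAP*

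**What the plan says.** SAP Section 2.1.3.1 makes NC a co-primary endpoint and gives its recording frequency: "The NC score is assessed by the patient on a daily basis from V1 and throughout the study". For the analysis, "the average of all scores from the preceding 4 weeks to the corresponding visit will be used as the analysis score for that visit".

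SAP Section 2.5.2, under "Periodical average of daily efficacy endpoints at designated study days", states that "the time period used to calculate the periodical average at each designated study day is summarized in" Table 2. The first column of that table covers the morning total symptom score and its components, nasal congestion among them. The periods up to Week 24 are Days 2-29, 30-57, 86-113 and 142-169. After that, within the treatment period, they are Days 254-281 and 338-365. Day 1 is the day of randomization. Neither document defines these averages for any other period.

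For patients who stop treatment without rescue, SAP Section 2.4.4.1 says that "a multiple imputation approach will be used to impute missing Week 24 value". One method is described for each co-primary endpoint, but the code is a sample for the nasal polyp score only. Its variable list begins "var asthma surgery region treatment basenps chg4nps chg8nps" and continues with the changes at Weeks 16 and 24. No variable list is given for NC. SAP Section 2.4.4.2 carries the method over to Week 52.

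**The concern.** The Table 2 time points up to Week 24 are the endoscopy visits. Endoscopy needs a visit, so the polyp score has no other post-baseline values to offer. A daily diary does.

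If NC is imputed from its Table 2 averages, as the polyp-score code suggests, a patient whose diary ends at Week 20 has Week 24 imputed from Weeks 4, 8 and 16. The four weeks of diary next to the missing period were collected but are not used. They are likely to be strong predictors. They would also let the model see a worsening just before the diary stops, which makes the missing-at-random assumption easier to defend. What is at stake is precision and the plausibility of the imputation for a co-primary endpoint, and for Week 52 NC, which is in the testing hierarchy.

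**Working it through.** **Inputs.** Averaging periods, and Day 1 as randomization: SAP Section 2.5.2, Table 2. Daily recording: SAP Section 2.1.3.1. Imputation visits: the sample code in SAP Section 2.4.4.1. The correlations between 4-week averages are not in the documents and are assumed to be 0.7-0.9.

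**The plan's own figure.** The binary NC analysis in SAP Section 2.4.4.1 gives Days 142-169 as 28 days: 169 - 142 + 1 = 28, reproduced. The other three periods to Week 24 are also 28 days each.

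**Coverage to Week 24.**
- Post-baseline diary days: 169 - 2 + 1 = 168.
- Days in an average: 4 × 28 = 112.
- Days in none: 168 - 112 = 56, namely Days 58-85 (28) and 114-141 (28). Share: 56/168 = 33.3%.
- Counting only days before the Week 24 window (Days 2-141): 56/140 = 40%.

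**Coverage from Day 170 to Day 365.**
- Diary days: 365 - 170 + 1 = 196, or seven 28-day blocks.
- Days in an average: 2 × 28 = 56.
- Days in none: 140 (71%), the blocks 170-197, 198-225, 226-253, 282-309 and 310-337.

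**Distance from the missing value.** If the diary stops on Day 141, the last average ends on Day 113, so the final 28 collected days are unused. If it stops on Day 337, the last average ends on Day 281, so the final 56 are unused.

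**Effect on a missing Week 24 value.** Number the six 28-day blocks to Week 24 from 1 to 6, with total variance 1. The planned predictors are blocks 1, 2 and 4. The alternative is blocks 1 to 5.
- First-order autoregression: only the latest block matters, so the residual variance is 1 - ρ⁴ from block 4 and 1 - ρ² from block 5.
- Compound symmetry with k predictors: 1 - kρ²/(1 + (k - 1)ρ), with k = 3 against k = 5.

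| ρ | Autoregressive: planned | All blocks | Cut | Compound symmetry: planned | All blocks | Cut |
|---|---|---|---|---|---|---|
| 0.7 | 0.760 | 0.510 | 33% | 0.388 | 0.355 | 8% |
| 0.8 | 0.590 | 0.360 | 39% | 0.262 | 0.238 | 9% |
| 0.9 | 0.344 | 0.190 | 45% | 0.132 | 0.120 | 10% |

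The percentages come from unrounded values. The illustration leaves out the baseline score and the stratification factors, which are also in the imputation model. It applies only to unrescued patients with diary data through Days 114-141 and none in Days 142-169.

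**The case against.** The case for leaving the plan alone has four parts.

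- **The imputation reading is an analogy.** The code is labelled a sample and its variables are polyp scores. This stands as a caveat. But the SAP states one method for each co-primary endpoint and defines no other NC averages, so Weeks 4, 8 and 16 is the natural reading.
- **Few patients are affected.** The averaging rule sets no minimum number of entries, so a few entries in Days 142-169 appear to give an observed value. Protocol Section 10.3.1 keeps patients on the diary after they stop treatment, and the SAP uses off-treatment data. This stands, and it is why the gain is modest. The documents do not allow the number of patients to be estimated.
- **The large variance cut depends on the correlation structure.** This also stands. The documents support neither structure, so the full range has to be quoted.
- **Power is not in danger.** The SAP states 99% power for NC with 25% dropout. That is fair: the point concerns the quality of the imputation, not whether the trial can succeed.

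A reader might infer more: that the worst-observation rule for rescued patients also cannot use Days 58-85 or 114-141, and so understates worsening before rescue. The documents do not establish this. SAP Section 2.4.4.1 refers to the worst post-baseline value up to surgery or steroid use, without saying whether that is a Table 2 average, an average ending at rescue or a daily score. The last two would include those days.

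Nor would adding blocks to that rule be neutral. With stable scores and the same assumed correlations, the worst of five blocks exceeds the worst of the three planned blocks by 0.10-0.20 SD on average in simulation, with no true deterioration. If rescue is more common on placebo, as the protocol's sample-size section assumes (15% against 5%), this could enlarge the apparent effect. That is a trade-off, not a free improvement.

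**Conclusion.** The point holds for the multiple imputation. The two gaps before Week 24 and the five after it follow directly from Table 2. That NC would be imputed without those days follows from Table 2 together with the sample code, by analogy.

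The benefit of closing the gaps is modest. For the patients described above, the residual variance of Week 24 NC falls by somewhere between 8-10% and 33-45%, depending on an assumed correlation structure at assumed correlations of 0.7-0.9. No size was worked out for Week 52, where the share of unused days is larger. A patient with an observed, unrescued Week 24 or Week 52 value is unaffected. Nothing here shows bias in favour of dupilumab, and no conclusion is drawn about the worst-observation rule. This is a worthwhile improvement, not a defect that threatens the primary analysis.

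**What to change.** Before database lock, amend SAP Sections 2.5.2 and 2.4.4.1 as follows.

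1. Derive 28-day averages of the diary endpoints (NC, loss of smell, total symptom score and its rhinorrhea components) for Days 58-85 and 114-141, and for Days 170-197, 198-225, 226-253, 282-309 and 310-337.
2. Use them only as additional predictors in the multiple imputation of these endpoints, and list the imputation variables for NC explicitly.
3. Leave the analysis time points unchanged, so that the repeated-measures sensitivity model gains no visits. Do not add the new averages to the values from which the worst observation is taken.

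The cost is derived variables from data already collected, a short SAP edit and a larger imputation model. On the Table 2 reading, the earlier post-baseline values rise from 3 (Weeks 4, 8, 16) to 5 for Week 24, and from 5 (Weeks 4, 8, 16, 24, 40) to 12 for Week 52.

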2.5.3 Missing data

For categorical variables, patients with missing data are not included in calculations of percentages unless otherwise specified. When relevant, the number of patients with missing data is presented.

Handling of computation of treatment duration if investigational medicinal product end of treatment date is missing For the calculation of the treatment duration, the date of the last dose of IMP is equal to the date of last administration reported on the end-of-treatment case report form page. If this date is missing, the exposure duration should be left as missing.

The last dose intake should be clearly identified in the case report form and should not be approximated by the last returned package date.

Handling of medication missing/partial dates

No imputation of medication start/end dates or times will be performed. If a medication date or time is missing or partially missing and it cannot be determined whether it was taken prior or concomitantly, it will be considered a prior, concomitant, and posttreatment medication.

Handling of adverse events with missing or partial date/time of onset

Missing or partial adverse event onset dates and times will be imputed so that if the partial adverse event onset date/time information does not indicate that the adverse event started prior to treatment or after the treatment-emergent adverse event period, the adverse event will be classified as treatment-emergent. No imputation of adverse event end dates/times will be performed. These data imputations are for categorization purpose only and will not be used in listings. No imputation is planned for date/time of adverse event resolution.

Handling of adverse events when date and time of first investigational medicinal product administration is missing

When the date and time of the first IMP administration is missing, all adverse events that occurred on or after the day of randomization should be considered as treatment-emergent adverse events. The exposure duration should be kept as missing.

The last dose intake should be clearly identified in the case report form and should not be approximated by the last returned package date.

Handling of missing assessment of relationship of adverse events to investigational medicinal product

If the assessment of the relationship to IMP is missing, then the relationship to IMP has to be assumed and the adverse event considered as such in the frequency tables of possibly related adverse events, but no imputation should be done at the data level.

Handling of missing severity of adverse events

If the severity is missing for 1 of the treatment-emergent occurrences of an adverse event, the maximal severity on the remaining occurrences will be considered. If the severity is missing for all the occurrences, a “missing” category will be added in the summary table.

Handling of potentially clinically significant abnormalities

If a patient has a missing baseline he will be grouped in the category “normal/missing at baseline.”

For PCSAs with 2 conditions, one based on a change from baseline value or a normal range and the other on a threshold value, with the first condition being missing, the PCSA will be based only on the second condition.

For a PCSA defined on a threshold and/or a normal range, this PCSA will be derived using this threshold if the normal range is missing; eg, for eosinophils the PCSA is > 0.5 GIGA/L or $>ULN$ if $ULN \geq 0.5$ GIGA/L. When ULN is missing, the value 0.5 should be used.

Measurements flagged as invalid by the laboratory will not be summarized or taken into account in the computation of PCSA values.

